**Table 6. Schedule of assessments.**

	Screening	BL	Wk 1	Wk 2	Wk 3	Wk 4	Wk 5	Wk 6	Wk 7	Wk 8	Wk 9	Wk 10	Wk 11	Wk 12	FU 1
Quick Screen	X														
MINI	X														
Urine pregnancy test	X	X				X				X					X
C-SSRS	X	X	X	X	X	X	X	X	X	X	X	X	X	X	X
SBQ-R	X														
Daily Substance Use Logs and Time-Line Follow-Back	X	X	X	X	X	X	X	X	X	X	X	X	X	X	X

MCQ	X	X	X	X	X	X	X	X	X	X	X	X	X	X
Urine Drug Test	X	X	X	X	X	X	X	X	X	X	X	X	X	X
Urine cotinine	X	X	X	X	X	X	X	X	X	X	X	X	X	X
CWS	X	X	X	X	X	X	X	X	X	X	X	X	X	X
PROMIS-29	X				X				X					X
DSM-5 Criteria for CUD	X					X			X					X
Self-Efficacy Questionnaire	X													X
Marijuana Problem Scale	X													X
Reasons for Quitting Questionnaire	X													
Review of AEs			X	X	X	X	X	X	X	X	X	X	X	X
Pill Count			X	X	X	X	X	X	X	X	X	X	X	X
Med Video Adherence			X	X	X	X	X	X	X	X	X	X	X	

**Screening and Diagnostic Instruments.** **Quick Screen:** This assessment will be used to quickly determine whether an individual meets inclusion or exclusion criteria for the study when they first present. The instrument is designed to assess for substance dependence and obvious psychiatric, medical, and logistic exclusions. **Mini-International Neuropsychiatric Interview (M.I.N.I.):** The M.I.N.I. is a brief structured interview that was designed to assess DSM-5 diagnoses using a series of questions in dichotomous format (yes/no) (Sheehan & Lecrubier, 2003; Sheehan et al, 1998).

**Psychiatric and Functioning Assessments.** **Columbia-Suicide Severity Rating Scale (C-SSRS):** The C-SSRS (Posner et al., 2011) is a brief, low-burden suicide assessment scale administered by a clinician. We have successfully used this instrument in multiple previous trials, and it is regarded as the gold standard of suicidality assessment in clinical trials. **Suicide Behaviors Questionnaire-Revised (SBQ-R):** The SBQ-R is a 4-item psychological self-report questionnaire designed to identify risk factors for suicide by assessing different dimensions of suicidality including lifetime suicide ideation and/or attempt, frequency of suicidal ideation over past 12 months, threat of suicide attempt, and likelihood of suicidal behavior in the future. **PROMIS-29:** This assessment, available through the Phen-X toolkit, includes 29 self-administered quality of life-type questions from the PROMIS® Profile 29 for adults. The quality of life questions include physical function, anxiety, depression, fatigue, sleep disturbance, ability to participate in social roles and activities, and pain intensity over the past 7 days. Each question, except for the pain intensity question, is measured on a 5-point scale.

**Daily Substance Use Logs.** Participants will be asked to complete daily report surveys through REDCap (Research Electronic Data Capture – a secure, web-based application designed exclusively to support data capture for research studies) during the study. The daily report will ask about cannabis and any other drug or alcohol use on the day prior, as well as (during the 12 weeks of treatment) times of medication dosing. Participants will be asked to begin completing daily reports following their screening visit. Links to access the daily report will be sent to participants through their mobile phone and their email address. Participants may complete daily reports on either their smartphone or on a computer.

**Substance-Related Instruments.** **Time-Line Follow-Back (TLFB):** The TLFB (Sobell & Sobell, 1992) is a calendar-based instrument designed to assess daily substance consumption. Although initially designed to assess alcohol use, we have successfully modified this instrument to assess for other drug use. Upon review of the participant's daily substance use logs, cannabis use will be recorded as times used per day, with each time being defined as cannabis use separated by an hour of no cannabis use, in order to standardize for different types of cannabis use (joints, bowls, blunts, etc.), as well as recorded as amount used per day. Nicotine and other substance use will also be assessed. **Urine Drug Testing:** The urine drug tests will be screened qualitatively for the presence of opioids, cocaine, amphetamines, and benzodiazepines. Urine cannabinoid tests will be performed using the AXSSYM® system from Abbott Laboratories. This assay is semi-quantitative with a

detection cut-off value of 30.00 ng/ml (Abbott AXSSYM® System package insert). Urine creatinine will also be obtained, as creatinine normalization has been proposed as a method to differentiate new cannabis use from residual drug excretion (Huestis and Cone, 1998; Schwilke et al, 2011). **Urine Cotinine:** Nicotine is metabolized to cotinine by the liver. Cotinine has a longer half-life than nicotine, and thus serves as a more reliable biomarker of cigarette smoking (Zevin et al., 2000). Urine will be screened qualitatively at each visit (detection cut-off value of 200 ng/ml). **Marijuana Craving Questionnaire (MCQ):** The MCQ (Heishman et al, 2001) is a Likert-based self-assessment of cannabis craving shown to be a valid and reliable instrument for measuring cannabis craving. The 12-item MCQ will be used, which has been constructed by selecting the three items from each factor of the full 47-item MCQ that exhibited the most within-factor reliability (Heishman et al, 2009). **Cannabis Withdrawal Scale:** The Cannabis Withdrawal Scale (Allsop et al, 2011) is comprised of 19 items for which participants rate severity of symptoms in the previous 24 hours. **Marijuana Use Summary Sheet/Self-Efficacy Questionnaire/Marijuana Problem Scale/Reasons for Quitting Questionnaire:** These worksheets, created by Stephens and colleagues (2000), will be used to gather information from participants to prepare personalized feedback reports (PFRs) for use in the motivational enhancement sessions. **DSM-5 Criteria for CUD:** DSM-5 criteria will be assessed at four time points to determine changes in severity of cannabis use disorder.

**Safety Assessment. Review of Adverse Events:** Adverse events (AEs) will be assessed weekly by study personnel. The type of AE, severity of AE, and the relationship to study medication will be recorded. AEs will be coded on a weekly basis using Medical Dictionary for Regulatory Activities (MedDRA) rules.

**Adherence.** During the 12 weeks of treatment, participants will be asked to record and upload twice-daily videos of medication-taking at home or in a private location of their choosing. These videos will be taken remotely and submitted via REDCap surveys to confirm medication adherence. Participants may use their personal mobile phones for video submission. If they do not have a smartphone, one will be loaned to them during the first week of study. Video submissions may only be completed on a smartphone (cannot be completed on a computer). A survey link will be sent to the participant via text message. Video capture will occur as part of the REDCap survey. Videos are automatically stored on Android smartphones, and participants will be informed of that so they can delete the files, if necessary. Participants using iPhones (and using loaner iPhones from our group) will not have stored videos on their phone and nothing will need to be deleted. These procedures were used successfully in the prior UG3 study. To complement these procedures, pill counts will be completed at each clinic visit during active treatment.

**Follow-up plan.** Following the study, participants will be referred for appropriate substance use management. In the event that an AE occurs during the study, a participant will be followed until resolution.

### **Statistical Analysis**

**Data Management Plan.** All data will be entered into a standard software package (REDCap). Macro programs will be written to check the data for logical consistency and values out of possible range. Quarterly database management and data integrity audits will be conducted.

**Baseline Analysis.** Categorical clinical and demographic variables will be assessed for balance between groups with chi-square tests of independence, while continuous variables will be assessed using Student's *t*-test. In addition to baseline group differences, preliminary analysis of baseline characteristics with cannabis use outcomes of interest will examine significant correlates of use reduction and abstinence. Characteristics found to be significantly associated with cannabis use outcomes will be included as covariates in the initial stages of adjusted statistical model development.

**Primary Analysis.** The primary aims for the UH3 portion of the protocol are to test the efficacy and safety of varenicline for CUD during a 12-week placebo-controlled trial. **Specific Aim 1:** The primary efficacy outcome is cannabis use reduction as measured by daily substance use logs and examined as the total number of use sessions at each weekly visit (primary interest weeks 6-12). Group differences in reported session use will be examined utilizing a generalized mixed effects models using a log-linear framework for count data. A Poisson distribution will be assumed with a logarithm link function will be used to assess the effects of varenicline treatment, time, and the appropriate interaction. Overdispersion in discrete count models can have a significant

impact on parameter inference, thus when detected, a negative binomial distribution will be specified and model fit will be compared to the Poisson model. An offset variable will be included in the models to account for possible differences in between visit timing. Models will be computed both adjusted for design variables and for significant covariates and confounders found in the preliminary analysis. Working correlation structures will be independently compared using the quasi-likelihood under the independence model criterion statistic (QIC). Model based means will be used to construct the pairwise comparisons between groups. All design adjusted models will include baseline average use sessions, study visit, treatment group assignment and randomization stratification variables (smoking status and gender). Additional exploratory approaches (e.g., analysis excluding participants with <80% medication adherence, per protocol analysis, completers analysis) will be undertaken.

**Specific Aim 2:** We will also compare the frequency of treatment-emergent AEs between treatment groups using a non-inferiority analysis. Of particular interest will be AEs leading to medication discontinuation and the occurrence of treatment-related serious AEs (SAEs). We will specifically compare neuropsychiatric AEs and suicidality (C-SSRS) ratings by treatment group. We hypothesize that treatment with varenicline will not cause undue adverse events and will be non-inferior to the placebo group by a margin ( $\delta$ ) of no more than a 10% using the Farrington-Manning score test for non-inferiority.

**Exploratory Analysis.** **Exploratory Aim 1:** Negative affect will be measured weekly during study treatment and compared between groups using generalized linear mixed effects regression models. Model based means will be used to construct the pairwise comparisons between groups and treatment by time interactions will be included to assess differential response over time. **Exploratory Aim 2:** Further, we will assess the time varying relationship between changes in negative affect and cannabis use sessions. Cross lagged panel models will be used to assess the lagged effect of changes in negative affect on cannabis use and visa-versa. Models will also include the autoregressive and synchronous relationships between these variables over time. Models will evaluate the influence of study treatment and medication adherence on the relationship between negative affect and cannabis use through the inclusion of time variable and time invariate effects. If significant treatment effects exist, additional stratified analysis will be conducted to elucidate the magnitude and direction of the effect.

**Additional Data Analysis.** Logistic regression models will be used to assess end of study abstinence (7 day point prevalence abstinence at week 12 and continuous abstinence from week 6 to 12); primary analysis models will be reported both as design adjusted results as well as adjusted for significant clinical covariates. To comprehensively examine the longitudinal efficacy of varenicline, weekly cannabis abstinence will also be analyzed over the entire treatment course using generalized linear mixed effects regression models under a GEE framework. Between study visit cannabis use will be based on daily substance use diaries confirmed via Time-Line Follow-Back procedures. The number of treatment visits attended will be compared between groups using Poisson regression models, while the number of days retained will be assessed using Cox Proportional Hazards regression models. Medication adherence (REDCap video capture of medication-taking; pill counts), tobacco smoking status, and gender will be explored as potential moderators of study outcomes through model interactions. Craving and withdrawal from cannabis will be assessed between groups over time using generalized linear mixed effects models.

**Missing Data and Attrition.** Missing data in longitudinal studies can be a problematic feature but can be mitigated through study design considerations. In order to minimize missing data and study attrition, design simplification and enhanced communication between study staff and participants will be emphasized. We will make every effort to prevent attrition (e.g., phone/text visit reminders, participation compensation, reinforcing adherence to the study protocol). To assess the potential impact of missing data on the primary study hypothesis, sensitivity analysis will be completed (a) with all available data and (b) using methods of multiple imputation (Rubin, 1987). Multiple imputation will be implemented using fully conditional specification. Due to the possibly high rate of missing data near the end of the study treatment period (>10%), 100 imputation data files will be created to assure reasonable relative efficiency (Von Hippel, 2018).

**Power and Sample Size.** The proposed study is powered on the primary efficacy hypothesis that varenicline treatment, relative to placebo treatment, will yield reduced cannabis use during the crucial stages of study treatment (weeks 6-12). The UG3 portion of this study showed a moderate self-reported reduction of weekly use days between the varenicline and placebo group (Cohen's  $d=0.43$ ). We intend to improve the granularity of this measure by assessing, in more detail, the number of use sessions occurring on a daily basis using daily

substance use report logs. We anticipate the increased information will allow better precision in the estimated effect between randomized study groups. Assuming this, coupled with the more extended 12-week treatment compared with the truncated treatment phase in the prior UG3 proof-of-concept trial, results in a slightly increased effect size of  $d=0.5$ , a high correlation between measures taken over time on the same participant ( $p=0.95$ ) and a 5% type 1 error rate, 57 participants are necessary in each treatment arm to achieve adequate power (80%). Additionally, the UG3 noted a higher than expected attrition rate of 35%, thus we anticipate that, despite our best efforts and revised approach, attrition during the study could reach 35%. Thus to ensure that we have the appropriate sample, we will enroll and randomize **approximately 90 participants per group for a total sample size of approximately n=180**. This will allow us to detect a difference in cannabis use session of at *least*  $d=0.5$  between randomized study groups while accounting for up to 35% study attrition. Similar to adult varenicline phase III studies (Gonzales et al., 2006), for the primary safety analysis we will compare the frequency of all treatment-emergent AEs (defined as any AE occurring between treatment initiation and one week following treatment conclusion), SAE's between varenicline and placebo groups. A non-inferiority analysis will be utilized (Piaggio et al., 2006). With an estimated placebo treatment-emergent AE rate of 75% (Gonzales et al., 2006), 90% power and two sided  $\alpha = 0.05$ , within our proposed sample of **approximately 180 randomized participants** we will be able to detect a 10% non-inferiority margin in AE frequency between treatment groups if it exists.

**Design considerations.** *Comorbid tobacco use disorder.* Individuals using both cannabis and tobacco have worse cannabis use treatment outcomes. Although data from a large RCT in alcohol using individuals found an effect of varenicline on drinking outcomes regardless of tobacco use status (Litten et al., 2013), it is possible that a differential effect of varenicline will be found among tobacco and non-tobacco using individuals with CUD. Therefore, we propose to stratify randomization on this variable, and to examine comorbid tobacco use as a potential moderator in the statistical analysis as well as the impact of varenicline on tobacco use in this population. *Consideration of gender as a biological variable.* In contrast to findings for stimulant drugs, there does not appear to be a strong effect of menstrual cycle phase in response to cannabis (for review, see Terner and de Wit, 2006). However, our previous work revealed a significant gender by treatment interaction in individuals with CUD, with women randomized to buspirone having fewer negative urine cannabinoid tests than women randomized to placebo ( $p=0.007$ ), and men randomized to buspirone having significantly lower creatinine adjusted cannabinoid levels as compared to those randomized to placebo ( $p=0.023$ ) (McRae-Clark et al., 2015). These findings support the need to consider gender as a critical variable in treatment investigations; as such, gender will be explored as a potential moderator of treatment response.

**Timeline.** Following administrative review, two months are anticipated for transition to the UH3 component to allow for study start-up activities. 32 months will be needed for participant recruitment and data collection. The final two months will be used for data analysis. At a recruitment rate of approximately five to six participants per month (a rate achieved in our prior CUD pharmacotherapy trials), we should meet our target sample size.

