### **Inclusion Criteria**

- Meet DSM-5 criteria for cannabis use disorder and use cannabis at least 3 days per week in the last 30 days.
- Express interest in receiving treatment for cannabis use disorder and reducing use.
- Males and females at least 18 years of age.
- If female and of childbearing potential, must agree to use acceptable methods of birth control for the duration of the trial.
- Must consent to random assignment, and be willing to commit to medication ingestion.
- Must be able to read and provide informed consent.
- Must have body weight  $>110$ lbs (50kg) and have BMI between 18 and 35  $\text{kg}/\text{m}^2$
- Must function at an intellectual level and have knowledge of the English language to sufficiently allow for accurate completion of assessments.

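### Does the primary count model count diary days that were never recovered as days without cannabis use?

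*Combined protocol and SAP*

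**What the plan says.** In the Primary Analysis part of Statistical Analysis, under Specific Aim 1, efficacy is judged first on "cannabis use reduction as measured by daily substance use logs and examined as the total number of use sessions at each weekly visit", with main interest in weeks 6–12. It is analysed with a log-linear Poisson or negative binomial model. The offset is described by its purpose alone: "An offset variable will be included in the models to account for possible differences in between visit timing". No formula is given.

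The logs do not stand alone. Under Substance-Related Instruments, TLFB is a calendar-based record made after review of the logs, in which "cannabis use will be recorded as times used per day, with each time being defined as cannabis use separated by an hour". Table 6 schedules logs and TLFB together at screening, baseline, each of weeks 1 to 12 and follow-up. Additional Data Analysis adds: "Between study visit cannabis use will be based on daily substance use diaries confirmed via Time-Line Follow-Back procedures".

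Missing Data and Attrition reads "To assess the potential impact of missing data on the primary study hypothesis, sensitivity analysis will be completed (a) with all available data" and then names multiple imputation as the second approach. It does not say whether imputation is by day or by visit.

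For the covariates: "All design adjusted models will include baseline average use sessions, study visit, treatment group assignment and randomization stratification variables". The scale and averaging window of the baseline value are not stated. On the timing of the logs: "Participants will be asked to begin completing daily reports following their screening visit". The eligibility criterion is to "use cannabis at least 3 days per week in the last 30 days".

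**The concern.** Self-completed daily surveys will have missed days. Suppose the weekly total sums the recorded days while the offset is the log of the interval length. A day with no information then contributes one day of exposure and zero sessions, and is in effect scored as abstinent. In a week with five recorded days out of seven, the rate is understated by two sevenths.

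The missing-data section does not clearly catch this. A partly recorded week still has a total, so it would enter as observed unless imputation were done by day.

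The treatment comparison is at stake only if the loss differs between arms or depends on use. Equal random loss lowers both rates and leaves their ratio alone. Unequal loss biases the ratio in either direction.

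A secondary worry is the baseline covariate. With a log link, a raw average may fit less well than its logarithm. The logs also begin only after screening, whereas eligibility looks back 30 days.

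**Working it through.** **The plan's own figure.** The documents give no rate of missed or unrecovered days, so no stated figure bears directly on this point. The sample size fixes the scale for the simulations. With d = 0.5, two-sided 5% (sidedness assumed) and 80% power, a single measure needs 2 × ((1.960 + 0.842)/0.5)² = 62.8 per arm. Averaging seven weekly measures with first-order autoregressive correlation 0.95 multiplies the variance by 0.8926: 62.8 × 0.8926 = 56.05, so 57 per arm, as stated. Attrition of 35% gives 57/0.65 = 87.7, so 88, against about 90 planned. Completers would number 90 × 0.65 = 58.5; the simulations used 58 per arm. None of this depends on the offset.

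**Size of the distortion.** Let g be the share of log days missed in an arm and r the share of those that TLFB recovers. The unrecovered share is f = g(1 − r). With a calendar-length offset and days lost at random,

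estimated ratio = true ratio × (1 − f_v)/(1 − f_p).

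For assumed log gaps of 20% in one arm and 10% in the other:

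| TLFB recovery r | Unrecovered shares | Factor, 20% on varenicline | Factor, 20% on placebo |
|---|---|---|---|
| 0% | 20% and 10% | 0.80/0.90 = 0.889 | 0.90/0.80 = 1.125 |
| 50% | 10% and 5% | 0.90/0.95 = 0.947 | 0.95/0.90 = 1.056 |
| 80% | 4% and 2% | 0.96/0.98 = 0.980 | 0.98/0.96 = 1.021 |
| 100% | 0% and 0% | 1.000 | 1.000 |

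Equal shares give 1.000 at any level of recovery.

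**Effect on the test.** These are null simulations with 58 per arm, 49 days (weeks 6–12), an assumed mean of 2 sessions a day and a between-person log-SD of 0.7. With the calendar offset, rejection at nominal 5% was 5.6% with no gaps, 6.0% with unrecovered shares of 4% and 2%, 7.4% with 10% and 5%, and 13.5% with 20% and 10%. A separate set of runs gave 6.4% with no gaps and 15.7% at 20% and 10%, against 5.9% when the offset counted only days with data. The inflation is material only near zero TLFB recovery.

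**Gaps that depend on use.** In a further simulation heavier-use days were twice as likely to be missed, with unrecovered shares of 20% and 10%. The calendar offset gave 0.85, or 1.19 reversed. A recorded-days offset gave 0.96 or 1.05, so counting covered days removes most of the bias but not all.

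**Where unrecovered days would fall.** At an attended visit TLFB covers the interval since the last one. If a visit is missed and the next attended, the interval is longer and the planned offset adjusts for it. Days after the last attended visit have no weekly total. They are missing weeks, which the missing-data section addresses. What remains is a day inside an attended interval that the participant cannot reconstruct.

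**Baseline covariate.** In simulations with 58 per arm where log outcome rate is linear in log baseline (slope 0.5 to 1.0, log-SD 0.5 to 1.0), the variance of the treatment effect using raw baseline, relative to log baseline, was 1.018 to 1.380. That is at most about 13 power points in favour of logging. Where log rate is linear in the raw count, the same ratio was 0.986, 0.964, 0.900 and 0.332 at log-SD 0.5, 0.6, 0.8 and 1.0. At the last value logging triples the variance (1/0.332 = 3.0).

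**The case for a change.** The best case for a change is that missed logs are foreseeable, the plan has no rule for days that stay blank, and a few lines would supply one without new data. The daily log also collects dosing times, so participants who stop the medication may stop logging, and the risk section cites more nausea, insomnia and abnormal dreams on varenicline. The plan allows for 35% attrition and more than 10% missing data late in treatment, inside the primary window. An offset equal to the log of days with a recorded value matches the planned one when nothing is lost. Fixing it in advance would remove a choice that could otherwise be made after seeing the data.

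Part of this stands. The silence is real, the algebra is right, and imputing whole visits would not touch a partly recorded week. The rest is weaker. The mechanism for a difference between arms is inference, and attrition and late missing data mostly produce missing weeks, not blank days inside attended intervals. The larger ratios assume that TLFB recovers nothing, which is hard to square with a calendar interview at each visit. The calendar-length offset is itself only one reading of a sentence that states a purpose; counting the days covered since the last visit fits it equally well.

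**Conclusion.** No change to the plan is needed. The missing rule is a detail that an analyst building the weekly totals would have to settle and would settle sensibly: complete the logs from TLFB, and match exposure to the days covered. Bias requires three things together: unrecovered days within attended intervals, an imbalance between arms or dependence on use, and a calendar-length offset. The documents give evidence of none of them. If 80% of assumed 20% and 10% log gaps are recovered, the factor is 0.98 or 1.02 and the test's size is almost unchanged; with full recovery there is no effect. The conclusion rests on weekly TLFB filling most missed days. Near-zero recovery with a twofold difference between arms would matter (0.89 or 1.13), but the planned procedures make that unlikely.

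The baseline item gives no reason for change either. Its scale does not bias a randomised comparison, and the gain from logging reverses under another plausible functional form. A 30-day baseline would also need a TLFB session count over that period, which the protocol does not specify.
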